10 EFFICACY ANALYSES

Efficacy parameters will be listed and summarized for all implanted subjects, stratified by cancer type. There will be no formal hypothesis testing and no group comparisons are currently planned. The primary efficacy outcome will be all-cause mortality, as defined above in [Section 3.3.1](#).

Secondary efficacy outcomes will be:

- Time from first implantation to death
- Time from diagnosis of Stage IV disease to death
- Changes from baseline based on MRI, CT or PET-CT scan, and other appropriate imaging techniques (e.g., sonography, bone scans, other x-rays) as indicated, if feasible.
 - In primary and/or secondary tumor size (volume, area) and
 - In state (necrosis, vascularization) on MRI, CT or PET-CT scan, and other appropriate imaging techniques (e.g., sonography, bone scans, other x-rays) as indicated.
- Change from baseline in tumor markers (CEA, CA19-9)
- Change from baseline in CA125 (as a marker of inflammation)
- Changes from baseline in:
 - Clinician Global Clinical Assessment
 - Activities of daily living
 - Symptom rating
 - Quality of life (QCQ-C30)
 - Pain scale
 - ECOG

- Additional exploratory efficacy outcomes may be analyzed if feasible and will be defined in the CSR

10.1 Efficacy Outcomes

10.1.1 All-cause mortality

All-cause mortality for primary analysis is defined as time from date of the first scan showing disease progression after completion of prior treatment (time of origin, T_0) to death from any cause. Subjects still alive at the time of analysis will be censored at that time point.

Secondary analyses of time from first implantation to death, and time from diagnosis of Stage IV disease to death, will be analyzed similarly.

For all time-to-death analyses the Kaplan-Meier curves will be presented; respective 95% two-sided confidence intervals (CIs) will be calculated.

10.1.2 Changes in tumor size and state

All available measurements will be obtained from various radiological assessments

If available, the volume of all measureable lesions will be calculated as length x width x height. Observed values and changes from baseline in relationship to both first and most recent implant will be listed for each study time point at which these data are recorded. For continuous parameters, at each time point, observed values and changes from baseline will be summarized. Nominal outcomes will be categorized and summarized as frequencies and percentages of subjects at each time point. In listings, all available measurements of all lesions and malignant lymph nodes will be shown. For summaries, mean longest diameters, volumes, and densities for a given lesion / node class (e.g., target) for each subject will be calculated and summarized, if available and feasible.

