4 INVESTIGATIONAL PLAN

4.1 *Description of Overall Study Design and Plan*

This is an open-label clinical trial. The clinical trial will have duration of approximately 12 months and involve a potential total of four macrobead implants, each no less than three months apart.

Each subject will serve as his own control. This means that changes from baseline to various post-treatment time points will be analyzed for some variables (such as tumor markers, for example). The confidence intervals for these changes will be calculated. Of course, it is not planned for the survival analysis.

Seventy-four (74) male and female subjects with advanced pancreatic cancer or metastatic, treatment-resistant colorectal cancer meeting all the above inclusion criteria will be recruited and treated for the study. Baseline measurements will include tumor burden and size, tumor history and pathological diagnosis and grade, global clinical state, activities of daily living, symptom checklist including tumor-related symptoms, a sense-of-well-being scale, routine clinical biochemistry and any appropriate tumor markers as available, and an assessment of cellular and humoral immune status.

The primary tumor histopathology will be reviewed and will be evaluated with special staining to identify, if possible, the presence or absence of cancer stem cells and niche bodies.

The response of each subject to the intraperitoneal implantation of the RENCA agarose-agarose macrobeads will then be measured over the ensuing 3 months (and a 6, 9, and 12 months, if possible) with respect to changes in:

- Primary tumor size
- Size or number of secondary/metastatic tumors
- Tumor marker or relevant biochemical parameters such as liver enzymes, alkaline phosphatase, lactic dehydrogenase
- Cellular or humoral immune status
- Global clinical status or rating
- Performance status (Karnofsky PS and ECOG PS)
- Activities of daily living (ADL) rating
- Symptom rating/severity (including use of pain medications)
- Quality of life scale
- Circulating tumor cells (when possible)

After each successive implant, follow-up will be at Days 14, 30, 60, and 90. Because much of the testing will be objective in terms of quantifiable clinical laboratory and imaging testing, bias on the part of subjects, investigator, and analysts should be minimized.

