4.6 Assessments

The objective of the proposed Phase II study of the RENCA macrobeads is, as stated above, to determine the human clinical efficacy of the cancer macrobeads in advanced pancreatic and colorectal cancer. Responses will be

assessed according to the usual categories of complete or partial response (with specification of percentage), and none/progression (with specification of percentage). Response assessment will be measured in terms of changes in volume of primary tumor and number of metastases as assessed by CT or MRI; tumor marker PSA, as well as the physician global clinical assessment; performance rating scale (Karnofsky or similar); quality of subject life as measured by the EORTC Quality of Life Scale. Alkaline phosphatase and lactic dehydrogenase will also be followed.

Other laboratory determinations to monitor subject response to the implantation of the macrobeads will include detection of inflammatory responses (CBC with differential WBC and platelet count, erythrocyte sedimentation rate, C-reactive protein, amylase, immunological changes, and cytokine production), RT-PCR (polymerase chain reaction) specific to e-MuLV DNA, plasma viremia, and antibodies to normal murine antigens.

A critical and unique addition to the endpoints for assessing efficacy will be, where possible, a careful search for and identification of the niches of cancer stem and other cells within the niche bodies of the tumors the macrobeads are being used to treat. Markers of the niche bodies used to identify them and study their state (numbers, integrity of surround blood vessels, degree of stress) will include HLA, CD44+, CD133+, p27, Ki67, and the Tunel assay for apoptosis. Determination of the presence or absence of circulating tumor cells will also be made. When possible/available, pathology specimens will be examined for cancer stem cell niches.

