Where the evidence of such progression is questionable or unclear, review of the subject's condition and laboratory or imaging data (after the minimum period of nine weeks) as defined by the protocol and discussion with the subject and his/her primary physician/consultant(s) will be carried out with careful documentation of the discussions and any decisions or uncertainties. New bone lesions detected on bone scans at the end of the initial 90 days after implantation) may reflect pretreatment disease activity, and may not necessarily constitute disease progression unless confirmed by additional lesions developing subsequently. Hence, subjects will be evaluated for progression based on the following criteria: 1. Tumor progression with PET-CT/MRI assessments after every cycle). 2. Evidence of progression demonstrating the appearance of ≥ 2 new lesions. New lesions detected at the end of the initial implantation period and confirmed confirmation ≥ 6 weeks later. 3. Symptomatic progression (for subjects without measurable disease). Deterioration in ECOG PS of ≥ 2 units compared to baseline attributable to cancer in the opinion of the investigator. 4. Weight loss $\geq 20\%$ (NCI-CTCAE v 3.0, Grade 3) of the initial body weight attributable to cancer in the opinion of the investigator. 5. Other clinical events attributable to the cancer that in the opinion of the investigator require major interventions, such as surgical intervention for pain control. 6. Death from any cause. If in the opinion of the investigator, the subject has symptomatic improvement as measured by improvement in pain scales or narcotic analgesic consumption and there is evidence of bone scan or biochemical progression, he may be continued on treatment at the investigators discretion.

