16.2 Tables

Table #	Tables
14.1.1.1	Completion / withdrawal
14.1.1.2.1	Subject disposition, 1 implant
14.1.1.2.2	Subject disposition, 2 implants
14.1.1.2.3	Subject disposition, 3 implants
14.1.1.2.4	Subject disposition, 4 implants
14.1.2.1	Baseline characteristics
14.1.2.2	Contraception methods
14.1.2.3.1	Presenting oncology diagnosis
14.1.2.3.2	Previous oncology diagnosis
14.1.3	Con meds by drug class and preferred name
14.1.4	Number of Implantations and number of macrobeads implanted
14.2.1.1	Global Clinical Assessment
14.2.1.2	Activities of Daily Living
14.2.1.3	Quality of Life Scale (imputed)
14.2.1.3X	Quality of Life Scale (not imputed)
14.2.1.4.1	Pain Scale Assessment, Pain Level
14.2.1.4.2	Pain Location
14.2.1.5	ECOG
14.2.2.1	Tumor markers
14.2.2.2	Cytokines
14.2.3	Tumor size and state
14.2.4	Overall survival (from the most recent radiological scan showing evident disease progression to death)
14.2.5	Time from first implantation to death
14.2.6	Time from diagnosis of Stage IV disease to death
14.3.1.1.1	AE summary
14.3.1.1.2	Death summary
14.3.1.2	Treatment-emergent AEs by SOC
14.3.1.3.1	Treatment-emergent AEs by SOC and preferred term
14.3.1.3.2	Treatment-emergent AEs by severity
14.3.1.3.3	Treatment-emergent AEs by relationship
14.3.1.6	Treatment-emergent frequently reported ($\geq 2\%$ in all patients combined) AEs
14.3.2	Treatment-emergent SAEs by severity
14.3.4.1.1	Serum Chemistry Observed & Changes

Table #	Tables
14.3.4.1.2	Serum Chemistry, out of range flags
14.3.4.1.3	Serum Chemistry, Shift Table
14.3.4.1.4	Serum Chemistry Toxicity Grades
14.3.4.2.1	Hematology Observed & Changes
14.3.4.2.2	Hematology, out of range flag
14.3.4.2.3	Hematology, Shift Table
14.3.4.2.4	Hematology Toxicity Grades
14.3.5.1	Physical exam
14.3.6.1	Vital signs
14.3.6.2	Vital signs from diary
14.3.7	ECG

Mortality Figures	
16.2.6.4.1	Overall survival (from the most recent radiological scan showing progression)
16.2.6.5.1.1	Time from first implantation to death
16.2.6.5.1.2	Time from diagnosis of Stage IV disease to death

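### SAP 10.1.2 summarises tumor size as a per-subject mean over an undefined lesion class, with no sum, lesion count or new-lesion frequency, so the summary can move against tumor burden

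*SAP*

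**What the plan says.** Protocol 4.6 assesses response partly by "changes in volume of primary tumor and number of metastases as assessed by CT or MRI", alongside markers, clinical rating, performance and quality of life. Protocol 4.1 lists "Size or number of secondary/metastatic tumors" among the response variables. Protocol 5.8 includes a progression criterion that counts new lesions, at least two of them.

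The SAP's imaging outcome (sections 3.3.1 and 10) is change from baseline in size and in state. The size part reads "In primary and/or secondary tumor size (volume, area) and", and number is not mentioned.

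SAP 10.1.2 then does three separate things:

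- Measurement: if available, "the volume of all measureable lesions will be calculated as length x width x height".
- Listing: "In listings, all available measurements of all lesions and malignant lymph nodes will be shown".
- Summary: a per-subject mean within a class, with target given as the only example. The wording is that "mean longest diameters, volumes, and densities for a given lesion / node class (e.g., target) for each subject will be calculated and summarized".

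The section does not define the classes, say which class a new lesion joins, fix a lesion set at baseline, or give a value to a lesion that has disappeared. SAP 6.3 adds only that missing values are not imputed unless otherwise specified. The table list in SAP 16.2 has one relevant imaging table, 14.2.3, "Tumor size and state".

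**The concern.** The mean depends on two things at once: how large the lesions are, and which lesions are in the average. Only the first is the intended quantity. A small lesion joining the class pulls the mean down, and a small lesion leaving it pushes the mean up. Both shifts run opposite to the change in disease.

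SAP 3.2 says the trial's main focus is estimating parameters for planning later trials. A change-from-baseline estimate that can carry the wrong sign is a poor planning input, and this single-arm trial has no control group in which the same artefact would appear. SAP section 2 also notes that tumor measurements often cannot be obtained in these patients. The measured set may therefore change between visits for reasons unrelated to the tumor, and an unanchored mean would change with it.

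**Working it through.** The plan gives no figure to reproduce, and the documents give no lesion sizes, growth rates or new-lesion rates. All sizes below are illustrative assumptions. They show direction and do not predict this trial's data.

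**Condition for a false fall.** Take n baseline lesions with mean M, growth fraction g, and k new lesions of mean size d in the same class. The new mean is [nM(1+g) + kd]/(n+k). It is below M exactly when d < M - n·g·M/k.

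**New lesions in the same class**

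- One 5.0 cm lesion grows to 5.5 cm and two 1.0 cm lesions appear. Mean: (5.5+1.0+1.0)/3 = 2.5 against 5.0 cm, -50%. Sum: 7.5 against 5.0 cm, +50%. The threshold for d is 5.0 - 1×0.1×5.0/2 = 4.75 cm.
- Lesions of 40 and 30 mm each grow 20% and two 10 mm lesions appear. Mean: (48+36+10+10)/4 = 26.0 against 35.0 mm, -26%. Sum: 104 against 70 mm, +49%. With volume taken as the cube of diameter, mean volume is -13% and total volume +75%.
- For that 40/30 mm pair with 20% growth, the mean diameter falls if the new lesions average below 21 mm (one new), 28 mm (two) or about 30 mm (three).
- The sign is not always wrong. With one new 10 mm lesion, mean diameter is (48+36+10)/3 = 31.3 mm (-10%) but mean volume is +16%. With one new 30 mm lesion, mean diameter is 38.0 mm (+9%).

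**New lesions outside the class.** The 40/30 mm class goes to 48/36 mm, so its mean goes from 35 to 42 mm, +20%. The direction is correct, but the new lesions do not appear in that class's summary.

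**Lesion lost from a fixed class.** Lesions of 40 and 10 mm; the 40 mm lesion is stable and the 10 mm one vanishes. If the vanished lesion is dropped, the mean goes from 25 to 40 mm (+60%) while the sum goes from 50 to 40 mm (-20%).

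**Simulation** (20,000 subjects per setting)

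- *New lesions pooled.* Assumptions: 1 to 4 baseline lesions, lognormal with median 3 cm and log-SD 0.4; all grow 10%; a Poisson number of new lesions of 1 to 1.5 cm, all in the same class. Every subject's burden rises or, with no new lesion, still grows by 10%.

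| Average new lesions per subject | Mean diameter falls | Mean volume (cube) falls | Average change in mean diameter | Average change in sum of diameters |
|---|---|---|---|---|
| 0.5 | about 39% of subjects | 23% | +1% | +21% |
| 1 | 62% | 44% | -7% | +32% |
| 2 | about 85% | about 72% | -18% | +55% |

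- *Smallest lesion vanishes.* With 2 to 4 lesions, the smallest dropped from the average and the rest shrinking 10%, the mean diameter still rises in 64% of subjects.

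**The case against.** A reader might infer that under this SAP progression will read as shrinkage. The documents do not support that. The averaging is within a class, and nothing says a new lesion joins the class of the baseline lesions. The reference to all measurable lesions governs the volume calculation, and the reference to all lesions governs the listings; neither governs the summary. Under a target class fixed at baseline, new lesions cause no false fall.

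A reader might also infer that the SAP departs from the protocol's stated objectives. That too is unsupported. Protocol 3.1.1 and 3.2.1 name size and state without a count, Protocol 4.1 offers size or number as alternatives, and the SAP says it supersedes the protocol's statistical considerations. The mismatch is with the assessment text in Protocol 4.6 and the progression criterion in 5.8.

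Other points carry weight. New lesions remain visible in the listings. SAP 16.1 and 16.3 also plan a listing of time to radiologically evident progression and figures of radiographic PFS. The simulation percentages depend on assumed inputs and on pooling. A simple sum has its own hazard: if the 40 and 30 mm lesions both grow 20% and the second is not assessed, treating it as absent takes the sum from 70 to 48 mm, -31%, which is false shrinkage.

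These points make the false fall conditional and limit the severity, but they do not remove the fault. Listings are not the summarised endpoint, and the SAP text does not define the radiological progression event. The vanished-lesion distortion needs no pooling, and no reading of 10.1.2 yields a lesion count or a sum.

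**Conclusion.** The point holds in conditional form. The planned per-subject mean can move in the wrong direction when small new lesions share a class with baseline lesions, and when a small lesion vanishes and drops out, even from a fixed class. If new lesions are kept apart, the fault is omission: the class summary does not show new disease. The SAP does not say which case applies.

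The size cannot be stated for this trial. With the illustrative inputs, the mean and the sum differ in sign, by as much as -50% against +50% in the simplest example.

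Severity is should-fix. The SAP makes this a secondary summary, to be produced if feasible; all analyses are exploratory, no decision rule in the SAP uses mean lesion size, and all-cause mortality is unaffected. For pancreatic subjects, Protocol 3.2.1 places change in tumor size within its primary response rate. That adds a reason to correct the summary, but the SAP sets mortality as the primary outcome for both cancers.

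**What to change.** In SAP 10.1.2:

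1. Replace the per-subject mean diameter and mean volume by the sum over the lesions identified before the first implant, and define the lesion classes.
2. Score a vanished lesion as 0. When a baseline lesion was not assessed, set the sum to missing, or restrict the change to lesions measured at both visits and label it so.
3. Tabulate, at each time point, the lesion count and the number and percentage of subjects with any new lesion.
4. Report mean density only for baseline lesions that persist.

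The cost is SAP wording, some programming, matching of lesions across visits, and fewer subjects with an evaluable sum. Lesion measurements are already to be listed, but the documents do not show whether lesion identity across visits or a new-lesion flag is captured, so that should be confirmed first.

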10.1.3 Change in tumor markers and other biochemical parameters

See [Section 11.1.3](#) below for details on laboratory data collection and reporting. Clinical laboratory parameters will include the tumor markers CEA and CA 19-9. A tumor marker response is defined as a $\geq 20\%$ decrease from baseline in one or both of CEA or CA 19-9.

Other biochemical parameters include:

- Serum enzymes and proteins
- Kidney function (creatinine, blood urea nitrogen (BUN))
- C-reactive protein
- Hematology (leukocytes, hemoglobin, differential, platelets, erythrocyte sedimentation rate (ESR))
- Cytokines
- Cellular and humoral immunity status (observed values will be clinically reviewed to determine presence / absence of each antibody, etc.)
- CA125 is included as part of the assessment of inflammatory response to macrobead placement.

Along with listings and summaries, graphical displays of individual subject observed values over time will be produced for tumor markers, CA125, C-reactive protein, and ESR.

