No tumor-specific markers exist for pancreatic cancer; markers such as serum CA 19-9 have low specificity. Most patients with pancreatic cancer will have an elevated CA 19-9 at diagnosis. Following or during definitive therapy, the increase of CA 19-9 levels may identify patients with progressive tumor growth. The presence of a normal CA 19-9, however, does not preclude recurrence.

According to the National Cancer Institute (www.cancer.gov/cancerinfo/types/pancreatic), patients with any stage of pancreatic cancer can appropriately be considered candidates for clinical trials because of the poor response to chemotherapy, radiation therapy, and surgery as conventionally used. One such trial is the gemcitabine, docetaxel, capecitabine (GTX) therapy being utilized at Columbia University by [name] and his colleagues (Phase II).

Colorectal cancer:

In contrast to pancreatic cancer, cancer of the colon is a highly treatable and often curable disease when localized to the bowel. Surgery is the primary form of treatment and results in cure in approximately 50% of the patients. Recurrence following surgery is a major problem and is often the ultimate cause of death.

The prognosis of patients with colon cancer is clearly related to the degree of penetration of the tumor through the bowel wall, the presence or absence of nodal involvement, and the presence or absence of distant metastases. Beyond those characteristics, elevated pretreatment serum levels of carcinoembryonic antigen (CEA) have a negative prognostic significance. The fact is, however, that, even with good prognostic factors and aggressive chemotherapy with regimens such as FOLFOX and FOLFIRI, with or without the addition of bevacizumab and cetuximab (the latter for KRAS⁺ patients), many patients become resistant to available chemotherapies and targeted biological therapies. In addition, the other surgical and ablative techniques may no longer be applicable. With liver and lung metastases common problems, and brain metastases less common, but potentially devastating, there clearly is a need for new, more effective therapeutic measures, especially for those patients who do have metastatic spread of their tumors

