3.2.2 Secondary Objectives

1. To determine the safety and tolerability of the implantation of the RENCA cancer-cell-containing macrobeads in advanced pancreatic cancer subjects with respect to:
 - The peritoneum: irritation, inflammation, mechanical effects (over a period of at least 3 months);
 - Other intraperitoneal organs (liver, spleen, large and small intestines, kidney, bladder, omentum, etc.);
 - Local and systemic immune response (T and B cell/cellular, antibody responses);
 - Bacterial, viral zoonotic infection (clinical and hematological examination; PCR DNA analysis for viral DNA; specific viral antibodies);
 - Hypersensitivity reactions to murine antigens.
2. To determine progression, defined as the time from the first implantation until the first occurrence of any of the following events
 - a. Death due to any cause, or
 - b. Progression as defined by the presence of the occurrence of any three of the five following events:
 - i. An increase in the levels of tumor markers (e.g., CEA, CA19-9) of 50% from baseline determinations
 - ii. Radiographic progression including increase in primary or metastatic tumor size/volume; increasing metabolic activity of the presenting tumor or of new metastatic lesions on a PET/CT scan after the administration of radio-labeled fluorodeoxyglucose (FDG); and evidence of new metastatic lesions.

- iii. A decrease in the EORTC QLQ-C30 quality of life scale as compared to baseline of more than 25%;
(Above data will also be analyzed with censorship of deaths to further evaluate progression)
3. Determine overall survival (OS)
4. Circulating tumor cells will also be measured

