Each implant will be considered as Day 0. Post implant follow-up visits will be done in reference to the corresponding implantations i.e. Days 14, 30, 60 and 90 for each implantation.

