7.2 Determination of Response

All subjects will be evaluated for response. The Evaluation Team will be composed of the Investigators, and one outside physician. All of the clinical tests will be evaluated independently by each member of the Team for changes against the baseline findings. This evaluation will take place prior to each implantation or when the subject leaves the study. The individual subject's baseline established prior to the first implantation will be used for the entire study. A table will be constructed using the changes from baseline.

Outline of Response Rate				
TESTS	Baseline Prior to First Implantation	Results Prior to Second Implantation	Results Prior to Third Implantation	Results Prior to Fourth Implantation
Clinical Findings				
Symptoms				
Global Clinical Assessment				
Quality of Life				
Clinical Laboratory Tests (Abnormalities)				
Tumor Markers (Decrease)				
Imaging Studies (Evidence of Change, e.g., volume or area)				
CT				
PET				
MRI				
Rating Scale				
Major Improvement: 3				
Improvement: 2				
No Change: 1				

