6.4.1.2 Baseline

Individual baselines will be established for each implant. For a given parameter, baseline for each implant will be the last recorded observation prior to the implant.

6.4.1.3 Implant 1 / Study Day 0

The day of the first implant will be designated as Implant 1 / Study Day 0.

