11.1.3 Clinical laboratory evaluations

Hematology, coagulation, serum chemistry, serum pregnancy, urinalysis, immunology, immunophenotyping, and all other laboratory parameters including those listed in [Protocol Section 5.6](#) will be analyzed at multiple laboratory sites and will be delivered via hard-copy reports to the central data processing center (VSI). Laboratory test names and units of measurement will be standardized by VSI. For select parameters, study day, collection lab, date and time collected, normal range, observed value, change from baseline in relationship to both first and most recent implant, out-of-range flag, and Common Terminology Criteria for Adverse Events (CTCAE) v3.0 toxicity grade (if applicable) will be listed. Laboratory observations with Grade 3 or higher toxicity and/or reported as an AE will be listed. For all parameters, study day, date collected, observed value, normal range, and out-of-range flag will be output to a spreadsheet. For select parameters, observed values and changes from baseline (in relationship to both first and most recent implant) will be summarized for each time point at which laboratory data were collected. Separate series of tables will show numbers and percentages of subjects by out-of-range flag and by toxicity grade. Shift tables will be provided that show numbers and percentages of subjects with normal ↔ abnormal shifts based on out-of-range flags and/or toxicity grades from baseline (in relationship to both first and most recent implant) to each subsequent time point at which laboratory data are collected.

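### Tumor marker response needs only a 20% fall in CEA or CA 19-9, with no condition on baseline level, the other marker or confirmation, so subjects without true benefit can be counted as responders

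*SAP*

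**What the plan says.** SAP section 10.1.3 defines marker response in one sentence: a fall of at least 20%, expressed as a "decrease from baseline in one or both of CEA or CA 19-9". Nothing elsewhere in the SAP or protocol adds to it.

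- **Baseline level.** Eligibility (protocol 4.3) sets no marker level. A rising marker is only one of the ways to show progressive disease at entry.
- **Which baseline.** SAP 6.4.1.2 resets it: "baseline for each implant will be the last recorded observation prior to the implant". Protocol 7.2 fixes it: "The individual subject's baseline established prior to the first implantation will be used for the entire study". SAP 11.1.3, to which 10.1.3 refers for laboratory reporting, uses both: "observed values and changes from baseline (in relationship to both first and most recent implant) will be summarized". Section 10.1.3 does not say which one the response uses.
- **Timing and confirmation.** Follow-up visits fall on "Days 14, 30, 60 and 90 for each implantation", and markers are drawn at each of them. SAP 6.4.3 keeps one value per visit window. No confirming sample is required, and the SAP does not say whether response is judged per visit or at any visit.
- **The other marker.** The only limit on a rise is in the protocol's pancreatic progression definition (3.2.2): "An increase in the levels of tumor markers (e.g., CEA, CA19-9) of 50% from baseline determinations". It is one of several events, of which three are needed for progression.
- **Laboratories.** SAP 11.1.3 says that laboratory parameters "will be analyzed at multiple laboratory sites" and that test names and units will be standardized. For select parameters it lists the collection laboratory and normal range, but the response rule uses neither.

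**The concern.** A responder rule built on one pair of measurements has to separate a real fall from ordinary fluctuation. This rule gives three routes to a favorable classification without benefit:

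- a fall in a marker that was never raised and so says little about that subject's tumor;
- a fall in one marker while the other climbs;
- a chance fall at a single visit.

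Having two markers and several visits multiplies the chances, and a chance fall can only add responders among subjects with no true change.

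The trial has no control group, so the false-response rate cannot be estimated and subtracted. SAP 10.2 prescribes exact 95% intervals for rates. Such an interval covers sampling error but not misclassification. SAP 3.2 says the trial is meant to estimate parameters for planning later studies, and an inflated marker-response rate could be carried into that planning.

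**Working it through.** **No stated figure to reproduce.** The documents give no expected marker-response rate, no false-response rate and no marker variability. What follows is a range under stated assumptions.

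**A case that needs no variability assumption.** Take illustrative values at one visit: CEA from 2.5 to 2.0 and CA 19-9 from 400 to 600.
- CEA: (2.0 − 2.5)/2.5 = −20%, so the subject is a responder under SAP 10.1.3.
- CA 19-9: (600 − 400)/400 = +50%, so the same visit meets the protocol's pancreatic marker-increase item.
- The rule gives the same answer whether or not the CEA of 2.5 lies within the laboratory's normal range.

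**Chance responses. Inputs:**
- threshold of 20%, either marker (SAP 10.1.3);
- one baseline value (SAP 6.4.1.2) and visits at Days 14, 30, 60 and 90 (protocol 4.1);
- *assumed:* total within-subject CV of 5% to 20%, log-normal variation, both markers measured and varying independently, no true change.

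**Formulas.**
- Log-scale SD: s = √ln(1 + CV²).
- One marker, one visit: p = Φ(ln 0.8 / (s√2)), because baseline and follow-up both vary.
- Either marker, one visit: 1 − (1 − p)².
- One marker, any of four visits sharing a baseline: P = 1 − ∫[1 − Φ(ln 0.8/s + z)]⁴ φ(z) dz. Either marker: 1 − (1 − P)².

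**Example at CV 10%.** s = √ln 1.01 = 0.0998. ln 0.8 = −0.2231. p = Φ(−0.2231/0.1411) = Φ(−1.58) = 0.057. Either marker: 1 − 0.943² = 0.11. For four visits P = 0.161, so either marker gives 1 − 0.839² = 0.30.

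The multi-visit figures were obtained by simulating 400,000 subjects per scenario and agree with numerical integration. The last column requires the same marker to be down at two consecutive visits.

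| Assumed CV | Either marker, one visit | Either marker, any of four visits | Same marker, two consecutive visits |
|---|---|---|---|
| 5% | 0.2% | 0.6% | under 0.1% |
| 10% | 11% | 30% | 6% |
| 15% | 27% | 58% | 20% |
| 20% | 38% | 71% | 32% |

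**If both markers truly rise by 10% per 30 days,** the any-visit probabilities at CV 10%, 15% and 20% are 8%, 29% and 47%. With confirmation they are 1%, 6% and 14%.

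The elevated-baseline and other-marker conditions were not simulated. Their effect depends on how many subjects have normal or discordant markers, which the documents do not give.

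**The case against.** The strongest reply is that little hangs on this rate. All-cause mortality is the SAP's primary outcome, and the listed secondary outcome is change from baseline in markers, not a responder proportion. No output is titled as a response rate, and all analyses are exploratory. This stands. SAP section 2 says response rate was modified because tumor measurements often cannot be obtained, and a reader might infer that marker response becomes the main measure of activity. No passage says so, and imaging change remains a secondary outcome where feasible.

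The size is also open to challenge. The CVs and the independence of the markers are assumptions, and at CV 5% the problem nearly disappears. SAP 11.1.3 summarizes laboratory values by time point, so the any-visit column should not be read as the SAP's own rule. This stands too, and it is why the full range is shown.

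Two further inferences are tempting and unsupported:

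- **Laboratory switching.** The multiple-sites statement covers the whole laboratory panel and may mean only that different tests go to different laboratories. There is one clinical site, and nothing shows one subject's CEA or CA 19-9 moving between laboratories. If it did happen, an assumed 10% between-laboratory CV would raise the any-visit figure at CV 5% from 0.6% to about 25%. That justifies a flag, not a finding.
- **Response and progression at once.** The 50% item applies to pancreatic subjects only and cannot establish progression alone. The worked case shows two marker criteria pointing opposite ways, not a subject who has both responded and progressed.

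The protocol's remark that "markers such as serum CA 19-9 have low specificity" is not evidence about within-subject variability. The same section says most pancreatic patients have elevated CA 19-9 at diagnosis, which makes the normal-baseline route less common for that marker in that group.

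The planned individual marker plots, and the listings if CEA and CA 19-9 are among the select parameters, would let a careful reader spot discordant cases. They would not change how those cases are counted.

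**Conclusion.** The concern holds in a limited form. Followed as written, SAP 10.1.3 counts a fall in an unelevated marker, a fall alongside a rising second marker, and an unconfirmed fall as responses. That follows from the words *one or both* and from the absence of any other condition. It supports saying that subjects without benefit **can** be counted as responders. It does not support saying that a known number **will** be.

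Under log-normal, independent variation with no true change and CVs from 5% to 20%, the false-response probability runs from 0.2% to 38% at one visit. It runs from 0.6% to 71% if any of four visits counts. The documents do not place the trial within that range. The mortality analyses are unaffected. The weight is that of an inexpensive improvement to an exploratory rate that should be made before the rate is reported or used for planning.

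**What to change.** Redefine marker response in SAP 10.1.3 so that all of these hold:

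1. A fall of at least 20% from the value before the first implant. State that this rate departs from the per-implant baseline in 6.4.1.2.
2. The falling marker was above the laboratory's upper limit of normal at that baseline.
3. The same marker shows the fall at two consecutive scheduled visits.
4. The other marker is not up by 50% or more at those visits. This limit is borrowed from the pancreatic progression item; say that applying it to colorectal subjects is a choice.

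For reporting:

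- Count subjects with both markers normal at baseline as not evaluable for this rate, and give their number.
- Keep treated subjects who die or withdraw before confirmation in the denominator as non-responders.
- Show the unconfirmed rate alongside.
- Flag any baseline and follow-up pair measured at different laboratories, using the collection-laboratory field, and add a sensitivity analysis without those pairs.

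**Cost.** Wording and programming. Marker values are collected, and collection laboratory and normal range are already listed for select parameters; confirm that CEA and CA 19-9 are among them. Fewer subjects will be evaluable and the rate will be lower. Subjects lost early cannot confirm, which matters where entry requires a life expectancy of only six weeks. Confirmation alone still leaves about 6%, 20% and 32% false responses at CV 10%, 15% and 20%.
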